- One of the great challenges in developing flavopiridol and applying it clinically has been determining its optimal dosing schedule. Following several different dosing schedules, one strategy that has been very promising in CLL is the application of so-called hybrid schedules of the drug (an infusion for an intermediate time following a bolus dose).

Objectives:

- Assess the toxicity and safety of administration of this hybrid schedule
- Assess the response rate of the hybrid schedule of flavopiridol in relapsed MCL and DLBCL

Eligibility:

- Relapsed MCL or DLBCL
- ECOG P.S. ≤ 2
- Age ≥ 18 years
- HIV serology negative

Design:

- Phase I/II
- Phase I portion consists of 3-4 dose levels of 3-6 patients each
- Administer weekly X 4 and then 2 weeks off (1 cycle). Restage after every 2 cycles. Continue if CR, PR or SD for up to 6 cycles. Dose reductions for toxicity will be addressed in the protocol.
- Phase II portion of the study will be a Simon optimal two-stage design: designed to rule out 20% response rate ($p_0=0.20$) in favor of a 45% response rate ($p_1=0.45$)
- The maximum sample size to be accrued for this study will be 71 patients.

TABLE OF CONTENTS

PRÉCIS	3
TABLE OF CONTENTS	4
1 INTRODUCTION	6
1.1 Study Objectives	6
1.2 Background and Rationale	6
2 ELIGIBILITY ASSESSMENT AND ENROLLMENT	11
2.1 Eligibility Criteria	11
2.2 Research Eligibility Evaluation	11
2.3 Patient Registration	12
3 STUDY IMPLEMENTATION	12
3.1 Study Design:	12
3.2 Drug Administration	13
3.3 Treatment Modifications:	15
3.4 Study Calendar	19
3.5 Off Study Criteria	21
3.6 Post Treatment Evaluation	21
4 SUPPORTIVE CARE	21
4.1 Tumor Lysis Syndrome	21
4.2 Anti-emesis	22
4.3 Neutropenia	22
5 DATA COLLECTION AND EVALUATION	22
5.1 Data collection	22
5.2 Data reporting	22
5.3 Response criteria	22
5.4 Toxicity Criteria	23
6 STATISTICAL CONSIDERATIONS	23
6.1 Data, Safety and Monitoring Board	24
7 HUMAN SUBJECTS PROTECTIONS	24
7.1 Rationale for subject selection	24
7.2 Evaluation of benefits and risks/discomforts	25
7.3 Risk/Benefit Analysis	25

7.4	Consent and assent	25
8	SAFETY REPORTING REQUIREMENTS/DATA AND SAFETY MONITORING PLAN	
	25	
8.1	Definitions.....	25
8.2	NCI-IRB and Clinical Director Reporting	25
8.3	CTEP Adverse Event Reporting Requirements	26
8.4	The Comprehensive Adverse Event and Potential Risks list (CAEPR).....	26
8.5	Adverse Event Characteristics	29
8.6	Expedited Adverse Event Reporting.....	29
8.7	Routine Adverse Event Reporting.....	31
8.8	Secondary AML/MDS	31

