2 ELIGIBILITY ASSESSMENT AND ENROLLMENT

2.1 ELIGIBILITY CRITERIA

- 2.1.1 Previously treated mantle cell lymphoma or diffuse large B-cell lymphoma (to include mediastinal (thymic) large B-cell lymphoma; transformed large B-cell lymphoma; follicular grade IIIB large B-cell lymphoma; intravascular large B-cell lymphoma)
- 2.1.2 Confirmed pathological diagnosis at the National Cancer Institute, NIH.
- 2.1.3 Recurrent measurable disease (measurable disease in 2 dimensions or leukemic disease which can be quantified and followed)
- 2.1.4 Prior anthracycline-based treatment for patients with DLBCL
- 2.1.5 Age > 18years
- 2.1.6 ECOG performance 2 or better
- 2.1.7 Major organ function: ANC > 1000/mcL, Platelet > 50,000/mcL, Creatinine < 1.5 mg/dL or creatinine clearance > 60 mL/min; SGPT < 5 x upper limit of normal; bilirubin < 2 mg/dL (total) except < 5 mg/dL in patients with Gilbert's syndrome as defined by > 80% unconjugated. ANC and platelet requirements must be met independent of transfusion.
- 2.1.8 Informed consent and willingness to use contraception by both men and women.
- 2.1.9 Both male and female patients must be willing to use adequate contraception (to include effective barrier methods of contraception) or to completely abstain from heterosexual intercourse while on protocol treatment.
- 2.1.10 Not pregnant or nursing because of an unknown potential for teratogenic or abortifacient effects
- 2.1.11 HIV serology negative. HIV positive patients receiving combination anti-retroviral therapy are excluded from the study because of possible pharmacokinetic interactions with flavopiridol. Additionally, the biology of HIV associated DLBCL's is often quite different from HIV negative disease due to involvement of EBV.
- 2.1.12 Hepatitis B surface antigen negative.
- 2.1.13 No active CNS lymphoma. These patients have a poor prognosis and because they frequently develop progressive neurological dysfunction that would confound the evaluation of neurological and other adverse events.
- 2.1.14 No history of inflammatory bowel disease unless this has been inactive for a period of 2 or more years.
- 2.1.15 Recovery from toxicity of prior therapy to a grade 1 or less.
- 2.1.16 No systemic cytotoxic or experimental treatments within 4 weeks of treatment.
- 2.1.17 No WBC > 100,000 cells/mcL

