3.2.2 Phase 2 Dosing

- Dose will be the MTD from the phase I portion.
- Administer weekly x 4 consecutive weeks, followed by 2 weeks without flavopiridol treatment for a cycle duration of 6 weeks (1 cycle).
- For all weeks of all cycles after cycle 1, patients will receive the dose administered on cycle 1, weeks 2-4.
- Administer up to 6 cycles if no disease progression.
- Restage all positive sites of disease after every 2 cycles, except bone marrow which should be repeated after other sites have achieved a CR.

3.2.3 Definition of Dose Limiting Toxicity:

Dose-limiting toxicity will be determined during the first cycle of treatment and is defined as:

- any grade 3 or greater non-hematologic toxicity excluding transient liver function abnormalities that resolve spontaneously within 10 days and/or transient electrolyte abnormalities that are not life-threatening, or fatigue
- grade 4 thrombocytopenia (< 25,000/mcL) persisting for 4 or more days

- grade 4 neutropenia ANC < 500/mcL persisting for 7 or more days despite the institution of G-CSF
- inability to continue with cycle 2 by 3 weeks after the end of cycle 1. Exceptions to this (i.e. accidents, family emergencies, etc) will be evaluated on a case-by-case basis.
- irreversible \geq grade 2 non-hematologic toxicity
- irreversible grade 3 thrombocytopenia at least possibly due to flavopiridol.
- And is a drug related event with an attribution of possible, probable or definite.

Patients with compromised bone marrow function from lymphoma will not be evaluable for hematologic related DLT. Irreversible is defined as lasting > 3 weeks. All toxicity will be evaluated and scored using NCI Common Terminology Criteria for Adverse Events (CTCAE) version 3.0 until December 31, 2010. CTCAE version 4.0 will be utilized beginning January 1, 2011.

3.3 TREATMENT MODIFICATIONS:

Patients should have recovered toxicities that are clinically significant and attributable to flavopiridol to grade 1 or baseline before beginning another cycle. If toxicity has not resolved to this level within 3 weeks from the end of the previous cycle, flavopiridol will be discontinued.

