5.3 RESPONSE CRITERIA

Response criteria for lymphomas as per Cheson criteria. [18] with modifications as described below. Responses must last for at least 4 weeks off treatment.

- Complete response (CR): Complete disappearance of all detectable clinical and radiographic evidence of disease and disappearance of all disease-related symptoms if present before therapy, and normalization of those biochemical abnormalities (e.g. LDH) definitely assignable to the lymphoma. All lymph nodes must have regressed to normal size (≤ 1.5 cm in greatest diameter if > 1.5 cm before therapy). Previously involved nodes that were 1.1 to 1.5 cm in greatest diameter must have decreased to ≤ 1 cm or by more than 75% in the sum of the products of the greatest diameters (SPD). Spleen, if considered to be enlarged before therapy, must have regressed in size and not be palpable on physical examination. The bone marrow must show no evidence of disease by

histology. Flow cytometric, molecular or cytogenetic studies will not be used to determine response.

- Complete response unconfirmed (CRu): As per CR criteria except that if a residual node is > 1.5 cm, it must have regressed by $> 75\%$ in SPD. Lymphocyte aggregates within the bone marrow must be negative for B-cell markers (e.g. L26).
- Partial response: $\geq 50\%$ decreased in SPD of 6 largest dominant nodes or nodal masses. No increase in size of nodes, liver or spleen and no new sites of disease. Splenic and hepatic nodules must regress by $\geq 50\%$ in the SPD. Bone marrow is irrelevant for determination of a PR.
- Definition of progressive disease (PD): Defined by at least one of the following: $\geq 25\%$ increase in the sum of the products of at least two lymph nodes, appearance of new lymph nodes, $\geq 50\%$ increase in the size of the liver and/or spleen as determined by measurement below the respective costal margin, appearance of new palpable hepatomegaly or splenomegaly that was not previously present, $\geq 50\%$ increase in the absolute number of circulating lymphocytes.
- Definition of stable disease: (SD) will be characterized by not meeting any of the criteria outlined above.

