8.6.3 Protocol-Specific Expedited Adverse Event Reporting Exclusions

CTCAE Category	Adverse Event	Grade	Hospitalization/ Prolongation of Hospitalization	Attribution	Comments
gastrointestinal	diarrhea	3	yes	any	
blood/bone marrow	neutrophils	4	no	any	
blood/bone marrow	lymphopenia	4	no	any	
blood/bone marrow	leukocytes	4	no	any	
metabolic	phosphate, serum-low	2-4	no	any	
metabolic	Albumin, serum-low	2-4	no	any	
metabolic	calcium, serum-high	2-3	no	any	
metabolic	calcium, serum-low	2-3	no	any	

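### A 50% rise in blood lymphocytes alone defines progression in every patient, leukemic or not, with no stated reference value, so a rise in normal cells can be called PD

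*Combined protocol and SAP*

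**What the plan says.** Section 5.3 (Response criteria) follows a cited lymphoma standard with modifications, and writes the PD list out in full. PD is "Defined by at least one of the following". The last item on the list is a 50% or greater "increase in the absolute number of circulating lymphocytes". It has no condition on the type of disease, no reference value (baseline or lowest count), no minimum count and no repeat. No other section adds one.

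Other parts of the protocol bear on this item:

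- Section 2.1.3 accepts "measurable disease in 2 dimensions or leukemic disease which can be quantified and followed", so leukemic disease is only one way into the trial.
- Section 5.3, at the end of the CR definition but in general words, states: "Flow cytometric, molecular or cytogenetic studies will not be used to determine response".
- The PR definition in section 5.3 has no lymphocyte item. SD is whatever meets none of the other definitions.
- The précis says "Continue if CR, PR or SD for up to 6 cycles", with restaging after every 2 cycles. Sections 3.2.1 and 3.2.2 say "Administer up to 6 cycles if no disease progression".
- Section 6 counts only PR or CR: at least 4 of 14 to continue an arm, and at least 8 of 25 to justify further development.

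The nodal PD item is a 25% or greater "increase in the sum of the products of at least two lymph nodes".

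**The concern.** In nodal MCL or DLBCL without circulating lymphoma cells, the blood lymphocyte count does not measure the tumor. The PD item still applies to those patients, and the results that could separate normal from malignant cells may not be used. A non-leukemic patient who goes from 400 to 600/mcL (600/400 = 1.5) meets PD as written, even while the nodes are shrinking.

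Response rate is a primary objective. PD can end treatment through the continuation rules. If it is called before a response is documented, or during the 4 weeks off treatment for which a response must last, the patient can be counted as a non-responder. The decision rules are small-count rules, so one or two such patients can change the outcome of an arm. The error works against the drug: it can make an active treatment look inactive.

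**Working it through.** **1. The text.** PD needs one item only. The lymphocyte item carries no restriction, while eligibility covers nodal and leukemic disease. It therefore applies to patients in whom it does not reflect the lymphoma.

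**2. The missing reference value matters.** Take an illustrative patient who starts at 600/mcL, falls to 400 on drug and returns to 600. Against baseline the ratio is 600/600 = 1.0, which is not PD. Against the lowest count it is 600/400 = 1.5, which is PD. The same data give two classifications.

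**3. The plan's own figures.** The inputs from section 6 are p0 = 0.20, p1 = 0.45, alpha = beta = 0.10, stop at 3 or fewer of 14, and success at 8 or more of 25.

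- P(early stop) = P(Bin(14, p) ≤ 3)
- P(success) = Σ over x = 4 to 14 of P(Bin(14, p) = x) × P(Bin(11, p) ≥ 8 − x)

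At p = 0.20, early stopping is 0.698 (the plan states 70%) and alpha is 0.093. At p = 0.45, early stopping is 0.063 and power is 0.903. The design reproduces.

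**4. How often an unchanged count could trip the item.** The documents give no within-person variability, so I assume a CV of 15-25%, independent log-normal counts, baseline as the reference and a single count at restaging. With s = √ln(1 + CV²),

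P(count ≥ 1.5 × baseline) = 1 − Φ[(ln 1.5 − ln m) / (s√2)],

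where m is the true on-treatment mean divided by the true baseline mean, and ln 1.5 = 0.405.

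| CV | s√2 | m = 1 (unchanged) | m = 0.8 (assumed 20% fall on drug) |
|---|---|---|---|
| 15% | 0.211 | z = 1.92, 2.7% | z = 2.98, 0.1% |
| 20% | 0.280 | z = 1.45, 7.4% | z = 2.24, 1.2% |
| 25% | 0.348 | z = 1.16, 12.2% | z = 1.81, 3.6% |

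The range is about 3-12% with unchanged counts, and 0.1-3.6% if the drug lowers the mean count by a fifth.

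**5. What a loss of responders would do.** Suppose a share f of true responders is classed as PD on lymphocytes alone. This f is assumed; it does not follow from step 4, because a loss also needs the reader to let PD override PR, or to stop treatment before a response is recorded. The observed rate is then 0.45 × (1 − f).

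| f | Observed rate | Wrong stage 1 stop | Power |
|---|---|---|---|
| 0 | 0.450 | 6.3% | 0.903 |
| 5% | 0.4275 | 8.7% | 0.863 |
| 10% | 0.405 | 11.7% | 0.811 |

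In a full arm, 25 × 0.45 = 11.25 responders are expected at p1, so f = 10% is about one responder (1.1). P(success) rises with p, so such losses cannot raise the type I error.

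**The case against.** The textual gap is hard to dispute. The case against its consequences is strong in several places.

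- **Certainty.** A reader might infer that a lymphocyte rise always ends treatment and always makes a non-responder. The text does not say so. PR has no lymphocyte item and no rule lets PD override it, so a patient with shrinking nodes could still be recorded as PR. The off-study list in section 3.5 does not name progression; the treatment consequence comes from the précis and sections 3.2.1 and 3.2.2. The word is *can*, not *will*.
- **Weekly counts.** The study calendar (section 3.4) schedules a CBC weekly during therapy. Treating each as a progression check would give 17-49% of patients with at least one hit over 12 counts, at the same assumed CVs. No section makes the weekly CBC a progression assessment. Tumor measurement is every second cycle and continuation is tied to restaging. Each 6-week cycle also has only 4 dosing weeks, so even the number 12 is doubtful. That range is not supported.
- **Drug-induced lymphopenia.** Section 8.4 lists a lymphocyte decrease as expected and section 8.6.3 exempts grade 4 lymphopenia without hospitalization from expedited reporting. It is tempting to treat this as making false PD more likely. Against baseline it does the opposite (step 4). It adds to the problem only if the reference is the lowest count.
- **Low starting counts.** Section 2.1.16 allows entry 4 weeks after cytotoxic treatment, but section 2.1.15 requires recovery from prior toxicity to grade 1 or less, which limits this argument.
- **The cited criteria.** They may contain limits that I cannot check. But the protocol applies them with modifications and writes out its PD list without any, so a reader would apply the list as it stands.

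These points reduce the size of the problem. They do not remove it: the population, the reference and the precedence remain unstated for a primary endpoint.

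**Conclusion.** The point holds as a defect in the definition of progression. As written, a 50% rise in lymphocytes is enough for PD in patients whose lymphoma is not in the blood, and the source of the cells may not be used to settle it. This can end treatment and can take a response out of the 4/14 and 8/25 counts, depending on how a reader fills the gaps.

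The size cannot be derived from the documents. The 3-12% rests on an assumed CV of 15-25%, unchanged true counts, baseline as the reference and one count at restaging. The fall in power from 0.90 to 0.86-0.81 rests on an assumed loss of 5-10% of true responders. Neither is a forecast.

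A separate and lesser point is that the nodal item refers to at least two nodes. Growth of a single measurable mass without new nodes can therefore default to SD; section 2.1.1 admits mediastinal large B-cell lymphoma, where this could arise. A reader might infer that this also distorts the 4/14 and 8/25 counts. It does not: SD and PD are both non-response, so it affects only PD classification and continuation.

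**What to change.** In section 5.3:

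1. Apply the lymphocyte item only to patients enrolled with quantifiable leukemic disease under section 2.1.3.
2. Name baseline as the reference for the 50% rise.
3. State whether PR or PD prevails when a patient meets both.
4. Reword the nodal item to cover one or more followed lesions (the separate, lesser point).

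Whether to require a confirmatory count is for the sponsor to decide. It must fit the visit schedule: a weekly repeat, for example, is not available in follow-up, where visits are every 3-4 months. Because PD governs continuation, any such requirement must also be reconciled with the continuation wording in the précis and sections 3.2.1 and 3.2.2.

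The cost is a few phrases, with no change to sample size, scans or blood tests. The downside is small: in a patient enrolled without leukemic disease, a progression seen only in the blood would have to be shown by another PD item.

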5.4 TOXICITY CRITERIA

NCI Common Terminology Criteria for Adverse Events (CTCAE) version 3.0 will be utilized for AE reporting until December 31, 2010. CTCAE version 4.0 will be utilized beginning January 1, 2011.

All appropriate treatment areas should have access to a copy of the CTCAE version 3.0 and CTCAE version 4.0. A copy of the CTCAE version 3.0 and CTCAE version 4.0 can be downloaded from the CTEP web site (<http://ctep.cancer.gov>) . Dose limiting toxicity is defined in section 4.2.

6 STATISTICAL CONSIDERATIONS

This will be a Phase I/II study.

- The Phase I portion of the study will have three to four treatment dose levels. Three to six patients will be accrued on each of the dose levels. Enrollment will proceed on the next dose level if 0 of 3 or 1 of 6 patients experience DLT. MTD will be defined as the highest dose level in which 0-1/6 patients experience DLT.
- The Phase II portion of the study will use a Simon optimal two-stage design in each of the two histology cohorts, MCL and DLBCL. For each of these two, the trial will be designed to rule out a 20% response rate ($p_0=0.20$) in favor of a 45% response rate ($p_1=0.45$). The justification for this is that other regimens could be associated with a 20% response rate and the objective is to demonstrate if this agent is superior to that level. With $\alpha=\beta=0.10$, the first stage for each histology would accrue 14 patients (28 total for the first stage, but by performing response evaluation on the 6 patients treated at the MTD in the phase I portion of the study and by counting them in each phase II arm according to their histology, this would only require 22 newly enrolled patients in the first stage). If 0-

3 of the 14 in a given arm have a PR or CR, then no further patients would be accrued. If 4 or more of the 14 patients in an arm have a CR or PR, then accrual would proceed to a total of 25 patients in that arm (11 more patients beyond the 14 in the first stage). If 4 to 7 have a PR or CR, then this is insufficient activity to warrant further investigation while 8 or more responses in 25 would be adequate to justify further development. Under the null hypothesis, 20%, the probability of early termination would be 70%.

- With up to 24 patients enrolled in the phase I portion, and 50 - 6 (6 are used for response evaluation from the phase I portion)=44 new patients potentially required for the phase II portion, a total of 24+44=68 total evaluable patients may be required if both arms need to go to the second stage. To allow for a small number of non evaluable patients, the accrual ceiling will be set at 71.
- To determine if patients have responded, they will be assessed every 8 weeks. The latest time for determining a response will be after 16 weeks or 4 cycles of therapy.
- It is expected that up to 3 years may be required to accrue up to 71 total patients permitted to enroll onto this trial.
- At this time, regarding correlative studies that will be performed such as microarray and proteomic analysis, we have not as yet identified how these markers and values are modified and changed by flavopiridol therapy. Hence, we do not plan a defined statistical analysis as this research is exploratory at this time.

6.1 DATA, SAFETY AND MONITORING BOARD

All data will be collected in a timely manner and reviewed by the PI and/or study chairman for toxicity. In the event that unacceptable toxicity occurs, the IRB and IND holders will be informed and appropriate measures as outlined in the study will be taken. The monitoring of this study will be done by the PI/Study Chairman and CTEP on an ongoing manner so a DSMB will not be used.

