3.1.1 Phase I Design

There will be 3-4 defined dose levels, with 3-6 patients treated at each dose level. The Phase I dose escalation will follow one of two different escalation rates shown in Tables 1 and 2. If DLT is observed in 0-1/6 patients on dose level 1, escalation will proceed according to Table 1. If DLT is observed in 2 of up to 6 patients on dose level 1, escalation will proceed according to Table 2. Escalation decision rules are shown below:

Number of Patients with DLT at a Given Dose Level	Escalation Decision Rule
0 out of 3	Enter 3 patients at the next dose level
≥ 2	Dose escalation will be stopped. This dose level will be declared the maximally administered dose (highest dose administered). Three (3) additional patients will be entered at the next lowest dose level if only 3 patients were treated previously at that dose.

1 out of 3	Enter at least 3 more patients at this dose level. 
• If 0 of these 3 patients experience DLT, proceed to the next dose level.• If 1 or more of this group suffer DLT, then dose escalation is stopped, and this dose is declared the maximally administered dose. Three (3) additional patients will be entered at the next lowest dose level if only 3 patients were treated previously at that dose. This rule does not apply to dose level one. Please see section 4.2
≤1 out of 6 at highest dose level below the maximally administered dose	This is the recommended phase 2 dose. At least 6 patients must be entered at the recommended phase 2 dose.

Entry onto a new dose level cannot occur until all patients on the previous dose level have completed cycle 1. The PI or his designee must be consulted regarding the proper dose level for all new patients. The definition of DLT is described in section 4.2.

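### Phase II has no study-level toxicity threshold or accrual-pause rule, so 22 to 44 new patients can be enrolled at a dose that may rest on 0-1 DLT in 6

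*Combined protocol and SAP*

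**What the plan says.** Section 6.1 has the investigator or study chairman review the data for toxicity. If toxicity is unacceptable, the IRB and IND holders are told and "appropriate measures as outlined in the study will be taken". The section does not define unacceptable or say where the measures are. Because the investigator and CTEP monitor the study continuously, it concludes "so a DSMB will not be used".

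The other relevant provisions are:

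- **Objectives (1.1.1).** Toxicity profile, DLT and MTD are primary, alongside response rate.
- **Phase I rule (3.1.1 and 6).** DLT counts govern escalation. "MTD will be defined as the highest dose level in which 0-1/6 patients experience DLT", and "At least 6 patients must be entered at the recommended phase 2 dose".
- **Phase II dose (3.1.2 and 3.2.2).** "Dose will be the MTD from the phase I portion". Neither section contains a cohort toxicity rule.
- **DLT definition (3.2.3).** "Dose-limiting toxicity will be determined during the first cycle of treatment". Treatment can run to six cycles.
- **Phase II accrual (6).** Each histology has a two-stage response design, and an arm stops at 0-3 responses in 14. The size is given as "50 - 6 (6 are used for response evaluation from the phase I portion)=44 new patients potentially required for the phase II portion".
- **Individual patients (3.3).** Holds, 20% reductions, discontinuation, removal from protocol and tumor lysis management, none of it limited to phase I.

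**The concern.** Section 6.1 relies on measures laid down elsewhere. In phase II, following that reference leads to rules for one patient at a time and to reporting duties. Nothing links the accumulated number of DLTs to whether the next patient is enrolled at the same starting dose.

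Six patients constrain a DLT rate very loosely, so an over-toxic dose can pass phase I by chance. Phase II is where this would first become visible. The response rule does not guard against it, because an active but over-toxic dose is the one that continues to full accrual.

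**Working it through.** **1. The plan's own figures.** Section 6 gives 14 then 25 patients per histology, with an arm stopping at 0-3/14.
- Early termination at a 20% response rate: the sum over x = 0 to 3 of C(14,x) × 0.2^x × 0.8^(14−x) = 0.698. The plan says 70%, so this reproduces.
- New phase II patients: 2 × 25 − 6 = 44 if both arms continue, and 2 × 14 − 6 = 22 if neither does. Then 24 + 44 = 68 evaluable patients, and 71 − 68 = 3 spare. All agree with the plan.

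**2. What 0-1 DLT in 6 establishes.** The limits below are the upper ends of exact two-sided 95% intervals.
- For 1/6, the rate p at which P(X ≤ 1 | 6, p) = 0.025 is p = 0.641.
- For 0/6, the upper limit is 1 − 0.025^(1/6) = 0.459.

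**3. Chance that a toxic dose meets the criterion.** The documents give no true DLT rate, so 40% is an assumption.
- P(X ≤ 1 | 6, 0.40) = 0.6^6 + 6 × 0.4 × 0.6^5 = 0.047 + 0.187 = 0.233.
- At other true rates: 0.66 at 20%, 0.42 at 30% and 0.11 at 50%.

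**4. Expected DLTs among new patients with no pause.**
- At 40%: 22 × 0.40 = 8.8 and 44 × 0.40 = 17.6.
- At 20%: 4.4 and 8.8. At 50%: 11 and 22.

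**5. Does the response rule substitute?** At a 45% response rate, P(0-3 of 14) = 0.063. An arm therefore continues with probability 0.94, whatever its toxicity.

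**6. A worked boundary.** Assume a limiting DLT rate of 1/3, a Beta(1/3, 2/3) prior, and a pause when the posterior probability that the rate exceeds 1/3 is above 0.80. After x DLTs in n patients the posterior is Beta(1/3 + x, 2/3 + n − x).
- With looks at every fifth patient from 10 to 40, the smallest counts that trigger a pause are 5/10, 7/15, 9/20, 11/25, 13/30, 15/35 and 16/40.
- For example, 5/10 gives 0.843 and 4/10 gives 0.643, while 16/40 gives 0.801.
- The exact probability of a pause over 44 patients comes from carrying the binomial distribution of the DLT count from look to look and removing paths that reach the boundary:

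| True DLT rate | P(pause) |
|---|---|
| 17% | 0.02 |
| 20% | 0.04 |
| 25% | 0.12 |
| 1/3 | 0.40 |
| 40% | 0.69 |
| 45% | 0.86 |

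- At 40%, the mean number treated before a pause or completion is 25 instead of 44, ignoring patients enrolled while DLT status is pending.

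**The case against.** A reader might infer that phase II has no measures against toxicity at all, or that its toxicity data cannot change the trial. The documents support neither reading. Section 3.3 applies in both phases, and under it doses are held, reduced or stopped in patients with toxicity. Section 6.1 requires toxicity review and notice to the IRB and IND holders, and section 8 adds expedited and continuing-review reporting. These bodies could act at their discretion. What is missing is a pre-specified study-level criterion.

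The size of the problem can also be overread. The 44 is a maximum. If both true response rates were 20%, both arms would continue with probability (1 − 0.698)² = 0.09 and neither with probability 0.698² = 0.49. The dose may also have more support than six patients: section 3.1.1 sets six as a minimum, and in Table 1 of section 3.2.1 levels 1 and 2 share the same dosing from week 2 onward, as do levels 3 and 4. This is why the point is that the dose may rest on 0-1 in 6.

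The worked boundary is open to challenge too. The plan declines 2/6 as an MTD, but at dose level 1 it lets 2/6 proceed under Table 2, and an observed 2/6 is not a stated limit on the true rate. The prior and the 0.80 cutoff are choices, and a cutoff of 0.90 with another prior gives different counts. These criticisms stand against the particular numbers. They do not supply the missing rule.

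**Conclusion.** The point holds as a gap at study level. In phase II the documents provide individual-patient measures, reporting and discretionary review, but no aggregate toxicity threshold and no accrual-pause rule. Between 22 and 44 new patients can be enrolled at a dose that may have been accepted on 0-1 DLT in 6, evidence that for 1/6 is compatible with a true rate up to 64%. At an assumed 40%, such a dose meets the 0-1/6 count 23% of the time, and about 9 to 18 DLTs would be expected with no pre-specified trigger.

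These figures assume independent patients with a common DLT rate and count cycle 1 only. They do not show that the dose is over-toxic, or that oversight would fail to notice if it were. The change is worth making because it is cheap and gives section 6.1 something definite to refer to.

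**What to change.** Add to section 6.1 a study-level boundary for phase II, using the cycle-1 DLT definition in section 3.2.3, that pauses accrual for review by the investigator, CTEP and the IRB. Refer to it in section 6. Section 5.2 records the protocol as completed with CTEP from Amendment J, so the text should say who takes CTEP's part after that.

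One usable boundary is 5/10, 7/15, 9/20, 11/25, 13/30, 15/35 or 16/40 DLTs among new phase II patients evaluable for DLT. The sponsor should confirm or replace the 1/3 limit and the 0.80 cutoff. Section 3.2.3 makes patients with marrow compromised by lymphoma non-evaluable for haematologic DLT, so the text must also say how they are counted.

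The cost is a short table and a running tally of data already collected. There would be a needless pause in about 2% of trials at a true rate of 17%, 4% at 20% and 12% at 25%. The limits are real:

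- It misses a 40% rate about 30% of the time.
- It does not cover toxicity after cycle 1.
- One DLT criterion can take 6 + 3 = 9 weeks to settle. With 71 patients spread evenly over 156 weeks, about 71/156 × 9 = 4 more would enroll meanwhile.

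The boundary triggers review only. It sets no dose and no patient-management rule.
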